3.1.6 Crossover for Subjects in Arm N

Subjects in Arm N may crossover to Arm N-I if all of the following criteria are met:

- The Safety Evaluation Phase for the N-I regimen has been completed and at least 6 subjects have been exposed to the dose level used for Stage 1 of the N-I regimen. In case Dose Level 2b has been activated and completed the safety assessment, subjects for cross over will be assigned to Dose Level 2 or Dose Level 2b after discussion between the sponsor and investigator taking into consideration previous safety and efficacy signals at these dose levels and the status of the individual subject planned for cross over.
- Subject has further disease progression (investigator-assessed RECIST 1.1-defined progression according to description provided in [Section 4.5.7](#), confirmed at least 4 weeks after the initial tumor assessment showing progression (definition of confirmed progression see [Appendix 3](#))) in the absence of clinical deterioration. For subjects with clear evidence of new or progressing brain metastases a confirmation is not required. These subjects may proceed with brain radiation therapy and, if necessary, with gamma-knife or surgical resection, after having completed the therapy a cross over to Arm N-I can be considered (see [Section 3.4.2.1](#)).
- Subjects with rapidly progressing tumors under nivolumab monotherapy may undergo radiation treatment first before initiation of the cross over after discussion between the sponsor and investigator.
- Subject has not experienced nivolumab related adverse events leading to permanent discontinuation as described in [Section 4.5.5](#).
- Subject is not continuing to derive any clinical benefit from nivolumab single agent therapy as assessed by the investigator which would allow continuation of nivolumab monotherapy (see [Section 4.5.8](#)).
- Subject is not a SCLC patient enrolled based on the Amendment 09 expansion.
- The individual case must be discussed with the medical monitor prior to cross over.

Subjects crossing over to Arm N-I will start treatment at Day 1 Week 1 as described for subjects originally randomized to Arm N-I. Subjects who crossed over and subsequently have an objective response in Arm N-I will not be considered in the decision making for Arm N-I proceeding to Stage 2. Subjects in Arm N-I cannot crossover to Arm N.

3.1.7 Re-exposure with Nivolumab/Ipilimumab for Subjects in Arm N-I

Subjects in Arm N-I may undergo a re-exposure with nivolumab/ipilimumab if they achieved an initial objective response (PR or CR) or stable disease of ≥ 3 months and had a subsequent documented progression. Subjects must fulfill the following criteria:

- Subjects have not experienced any related adverse events as described in [Section 4.5.5](#) (discontinuation criteria).
- Eligible subjects will receive up to four doses of nivolumab/ipilimumab (based on treatment assigned at randomization) during Re-exposure. Subjects can receive nivolumab monotherapy, if ipilimumab caused toxicities leading to its discontinuation ([section 4.5.5](#))

- Dosing may be delayed for toxicity (see [Section 4.5.2](#)).
- Subjects who have permanently discontinued study therapy for any reason and are in the follow up phase may not receive any re-exposure dosing.

3.1.8 Review of Safety

The subjects' safety will be monitored on an ongoing basis as described fully in [Section 7](#). Safety conference calls with investigators and representatives of the sponsor will be held approximately every other week with additional meetings as necessary. Decisions for the safety evaluation phase of Arm N-I and for continuing from Stage 1 to Stage 2 in both treatment arms will be made in conjunction with the investigators. In addition, a BMS medical safety team (MST) routinely reviews safety signals across the entire nivolumab program including combination studies with ipilimumab.

3.1.9 Treatment Beyond Progression

Treatment beyond investigator-assessed RECIST 1.1-defined progression will be permitted if the subject experiences investigator-assessed clinical benefit and the subject is tolerating the study treatment ([Section 4.5.7](#)). No treatment beyond progression with cobimetinib is permitted.

3.1.10 Inpatient Dose Reductions for Nivolumab, Ipilimumab and/or Cobimetinib

Inpatient dose reduction for nivolumab and/or ipilimumab is not permitted for any reason. Dose delays for the management of study treatment related adverse events are described in [Section 4.5.2](#).

Inpatient dose reductions for cobimetinib should be undertaken as presented in [Table 3.1.10-1](#) and based on the prescribing information.⁵⁷

Table 3.1.10-1: Recommended Dose Reductions for COTELLIC (Cobimetinib)

First Dose Reduction	40 mg orally once daily
Second Dose Reduction	20 mg orally once daily
Subsequent Modifications	Permanently discontinue cobimetinib if unable to tolerate 20 mg once daily

3.1.11 Mandatory Availability of Tumor Material

Tumor tissue from fresh tumor biopsies must be submitted prior to treatment for retrospective biomarker analyses. Tumor biopsies may be done during the screening period prior to study treatment start. Tumor material from biopsies done before the screening period is acceptable if the biopsy was performed within 3 months prior to the planned treatment start and no other systemic cancer therapy was administered in the meanwhile. Baseline tumor biopsies should preferably be performed from a tumor site that is NOT the only site of measurable disease. For subjects with only one site of measurable disease, tumor biopsies from this one tumor site are allowed if at least one of the following criteria is met:

- CT imaging performed after biopsy and there is still measurable disease or
- The type of biopsy is not expected to impact the measurability (eg, core needle biopsy) regardless on when imaging occurred, prior to or after biopsy.

3.1.12 Study Phases

This study will consist of three phases: screening, treatment, and follow-up.

Screening Phase:

- Begins by establishing the subject's initial eligibility and signing of the informed consent form (ICF).
- Subject is enrolled using the Interactive Voice Response System (IVRS).

Treatment Phase:

- Begins with the vial assignment call to the IVRS.
- A negative pregnancy test must be documented within 24 hours prior to the start of investigational product.
- Within 3 days from treatment assignment, the subject must receive the first dose of study medication:
 - **Arm N (nivolumab monotherapy):**
Nivolumab 3 mg/kg IV every two weeks (Q2W). See [Table 4.5-1](#)
 - **Arm N-I (nivolumab + ipilimumab)**
 - ◆ Dose Escalation Phase:

Staged Enrollment Phase: Dose Level determined in Dose Escalation Phase. See [Table 4.5-2](#) and [Table 4.5-3](#).

- **Dose Level 1**, Nivolumab 1 mg/kg IV combined with ipilimumab 1 mg/kg IV Q3W for 4 doses, then nivolumab 3 mg/kg IV Q2W. See [Table 4.5-2](#) and [Table 4.5-3](#).
- **Dose Level 2:** Nivolumab 1 mg/kg IV combined with ipilimumab 3 mg/kg IV Q3W for 4 doses, then nivolumab 3 mg/kg IV Q2W.

- **Dose Level 2b:** Nivolumab 3 mg/kg IV combined with ipilimumab 1 mg/kg IV Q3W for 4 doses, then nivolumab 3 mg/kg IV Q2W.
- **Dose Level 2c:** Nivolumab 3 mg/kg IV Q2W combined with ipilimumab 1 mg/kg Q6W.
- **Dose Level 2d:** Nivolumab 3 mg/kg IV Q2W combined with ipilimumab 1 mg/kg Q6W + cobimetinib 60 mg per os qd 21 days on/7 days off for the additional pancreatic cancer cohort only.

- Adverse event assessments will be documented at each visit throughout the study.

On-study laboratory assessments (after D1W1) should be drawn within 72 hours prior to dosing according to the schedule in [Table 5.1-2](#), [Table 5.1-3](#), [Table 5.1-4](#), and [Table 5.1-5](#).

- Women of child bearing potential (WOCBP) must have a negative pregnancy test documented as follows:
 - Arm N and Arm N-I2c: before every other nivolumab administration, within 24 hours prior to dosing.
 - Arm N-I: before every combined nivolumab / ipilimumab administration, within 24 hours prior to dosing. Thereafter every 4 weeks, within 24 hours prior to nivolumab dosing.
- PK samples and immunogenicity samples will be collected according to the schedule in [Section 5.5](#).
- Study drug dosing may be delayed for toxicity. See [Section 4.5.2](#).
- Treated subjects will be evaluated for response according to the RECIST 1.1 guidelines beginning 6 weeks (± 1 week) after first dose and continuing every 6 weeks (± 1 week) for the first 24 weeks, and then every 12 weeks (± 1 week) while on treatment or on treatment hold for any reason until disease progression (investigator-assessed RECIST 1.1-defined progression) or treatment discontinuation, except for subjects treated beyond progression or who discontinued treatment for other reasons than PD.

This phase ends when the subject is discontinued from study therapy. For a complete list of reasons for treatment discontinuation, see [Section 4.5.5](#).

Follow-Up Phase

- Begins when the decision to discontinue a subject from study therapy is made (no further treatment with study therapy).

Two follow-up visits include collection of PK/immunogenicity samples [Table 5.1-7](#), [Table 5.5.1-1](#), and [Table 5.5.1-2](#).

- Subjects who discontinue treatment for reasons other than tumor progression will continue to have tumor assessments beginning 6 weeks (± 1 week) after first dose and continuing every 6 weeks (± 1 week) for the first 24 weeks from first dose, and every 12 weeks (± 1 week) thereafter until disease progression (investigator-assessed RECIST 1.1-defined progression).

This does also apply to subjects whose treatment was put on hold after achieving confirmed CR or PR for more than 3 month (long lasting PR).

- Subjects will be followed for drug-related toxicities until these toxicities resolve, return to baseline or are deemed irreversible. All adverse events will be documented for a minimum of 100 days after last dose.
- Follow up visits should be made in-person. If a subject is unable to make an in-person visit, the reason should be clearly documented at the site.
- Follow-up visit 1 (FU1) = 35 days from the last dose \pm 7 days or coincide with the date of discontinuation (\pm 7 days) if date of discontinuation is greater than 42 days after last dose, Follow-up visit 2 (FU2) = 80 days (\pm 7 days) from follow-up visit 1.
- After completion of the first two follow-up visits, subjects will be followed every 3 months for survival via in-person visits, phone or email. Ad hoc survival data requests may be made during the study as well, particularly during database locks.

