1.3.2 Secondary Objective

- To assess the safety of nivolumab monotherapy, nivolumab combined with ipilimumab in subjects with advanced or metastatic tumors, or nivolumab combined with ipilimumab and cobimetinib in subjects from the additional pancreatic cancer cohort only.
- To assess Overall Survival (OS), OS-rate, Progression Free Survival (PFS), PFS-rate, and Duration of Response (DOR) with nivolumab monotherapy, nivolumab combined with ipilimumab in subjects with advanced or metastatic tumors, or nivolumab combined with ipilimumab and cobimetinib in subjects from the additional pancreatic cancer cohort only. PFS and DOR will be assessed by the BICR in selected tumor types.

[REDACTED]

[REDACTED]

[REDACTED]

[REDACTED]

[REDACTED]

[REDACTED]

[REDACTED]

[REDACTED]

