5.4 Efficacy Assessments

Study evaluations will take place in accordance with the flow charts in [Section 5.1](#). Baseline assessments should be performed within 28 days prior to the first dose utilizing CT or MRI. In addition to chest, abdomen, pelvis, and brain, all known sites of disease should be assessed at baseline. Subsequent assessments should include chest, abdomen, and pelvis, and all known sites

of disease and should use the same imaging method as was used at baseline. Subjects will be evaluated for tumor response beginning 6 weeks (± 1 week) from first dose and continuing every 6 weeks (± 1 week) for the first 24 weeks and every 12 weeks (± 1 week) thereafter, while on treatment or on treatment hold for any reason until disease progression and treatment discontinuation, whichever occurs later. Additionally, with the exception of crossover participants, tumor assessments will not be required upon initiation of subsequent anti-cancer therapy. Tumor assessments for ongoing study treatment decisions will be completed by the investigator using RECIST (Response Evaluation Criteria in Solid Tumors) 1.1 criteria ([Appendix 3](#)).

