5.9 Blinded Independent Central Review (BICR)

A Blinded Independent Central Review (BICR) will be performed for randomized subjects in selected tumor types to determine RECIST 1.1 response for the analysis of ORR, DOR, and PFS. Details of the Imaging responsibilities and procedures will be specified in the Imaging charter.

Sites will be informed of quality issues or the need for repeat scanning via queries from the central imaging vendor. Results of Central Imaging analysis will not be returned to the site.

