8.3.2 Secondary Endpoint(s)

The secondary objective (to assess the safety and tolerability of nivolumab monotherapy, nivolumab combined with ipilimumab in subjects with advanced or metastatic tumors, or nivolumab combined with ipilimumab and cobimetinib in subjects from the additional pancreatic cancer cohort only) will be primarily assessed by the rate of treatment-related AEs leading to drug discontinuations during the first 12 weeks of treatment. In addition, safety and tolerability will be analyzed through the incidence of adverse events, serious adverse events, and specific laboratory abnormalities (worst grade) in each cohort. Toxicities will be graded using the National Cancer Institute (NCI) Common Terminology Criteria for Adverse Events (CTCAE) version 4.0.

PFS is defined as the time from treatment assignment in IVRS to the date of the first documented tumor progression, as determined by the investigator or BICR for selected tumor types (per RECIST 1.1), or death due to any cause, whichever occurs first. Subjects who die without a reported prior progression will be considered to have progressed on the date of their death. Subjects who did not progress or die will be censored on the date of their last evaluable tumor assessment. Subjects who did not have any on-study tumor assessments and did not die will be censored on the date they were assigned treatment in the IVRS. Subjects who started anti-cancer therapy either prior to death or without a prior reported progression will be censored on the date of their last evaluable tumor assessment prior to the initiation of subsequent anti-cancer therapy.

OS is defined as the time between the date of treatment assignment in IVRS and the date of death due to any cause. A subject who has not died will be censored at the last known alive date. OS will be followed continuously while subjects are on the study drug and every 3 months via in-person or phone contact after subjects discontinue the study drug.

[REDACTED]

[REDACTED]

[REDACTED]

[REDACTED]

[REDACTED]

index.

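### In cohorts read by BICR, scanning stops at an investigator progression call the central reader may not share, so BICR PFS and DOR are expected to read somewhat too favourably

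*Protocol*

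**What the plan says.** Section 3.1.12 of the Protocol runs scans in the treatment phase "until disease progression (investigator-assessed RECIST 1.1-defined progression) or treatment discontinuation", "except for subjects treated beyond progression or who discontinued treatment for other reasons than PD". Subjects who stop for other reasons are scanned in follow-up on the same calendar, "thereafter until disease progression (investigator-assessed RECIST 1.1-defined progression"), so the investigator's call ends scanning there too. Section 3.1.5 ends treatment at that same call unless the subject is treated beyond progression.

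Section 5.4 words the stop differently: "until disease progression and treatment discontinuation, whichever occurs later", with no assessor named. It adds that, crossover participants apart, "tumor assessments will not be required upon initiation of subsequent anti-cancer therapy".

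The endpoint has another assessor. Section 1.3.2 states "PFS and DOR will be assessed by the BICR in selected tumor types", and Section 3.1.4 puts all SCLC expansion scans through BICR. Section 5.9 states "Results of Central Imaging analysis will not be returned to the site".

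On censoring, Section 8.3.2 states "Subjects who did not progress or die will be censored on the date of their last evaluable tumor assessment". Subjects who start anti-cancer therapy without prior progression are censored at the last evaluable scan before it. Death without prior progression is an event on the death date. Section 8.3.1 applies the same algorithm to DOR. Section 8.4.2.2 makes PFS a descriptive Kaplan-Meier summary.

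**The concern.** One assessor decides when scanning ends and another decides whether an event has occurred, and the first never learns what the second saw. A subject called PD by the investigator but not by the BICR leaves treatment and scanning with no BICR event. Kaplan-Meier then treats that subject as having the same outlook as everyone still under observation, although a physician has just judged the disease to be progressing.

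At stake are the BICR PFS medians, the 6- and 12-month PFS rates, and DOR, which Section 8.3.1 uses to characterise the primary endpoint. The SCLC expansion arms are open label, so discordance could also differ between them and affect how their two descriptive curves are read side by side.

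**Working it through.** **Step 1: follow one subject through the rules.** The investigator calls PD at a scheduled scan; the BICR does not.
- Treated beyond progression: scanning continues (3.1.12), so there is no problem.
- Stops treatment and starts new therapy: no further scan is required (5.4) and BICR PFS is censored at that scan (8.3.2).
- Stops, no new therapy, alive at cut-off: censored at that scan.
- Stops, no new therapy, dies: event at death, later than the next scan might have shown BICR PD.

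The Section 5.4 wording changes nothing here. The only PD the site knows is its own, and treatment ends there. The crossover exception gives no relief in the SCLC expansion, which is excluded from crossover (3.1.4, 3.1.6).

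**Step 2: inputs.** The scan calendar is from the Protocol: weeks 6, 12, 18, 24, then every 12 weeks. Discordance, uptake of new therapy, treatment beyond progression and median PFS are not in the documents and are assumed over ranges.

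**Step 3: size.** Two simulations compared 6-month Kaplan-Meier BICR PFS under the written rules with the value if scanning had run on to BICR PD.

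*Model A* (20,000 subjects per scenario; median PFS 8 or 13 weeks; BICR PD at each later scan with probability 0.7; 50 or 100% of discordant subjects start new therapy; death a median 13 weeks later; nobody treated beyond progression):
- 15% discordance: +3.5 to +4.3 points
- 25%: +6.0 to +7.6
- 35%: +9.1 to +11.7

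A repeat run gave about +4 to +13 overall.

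*Model B* (400,000 subjects per scenario; investigator PD one scan before BICR PD; median post-progression survival 4 months), selected results:

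| Median PFS | Discordance | New therapy | Treated beyond PD | Full scanning | As written | Shift (points) |
|---|---|---|---|---|---|---|
| 2 mo | 20% | 50% | 0% | 14.6% | 19.6% | +5.0 |
| 2 mo | 20% | 50% | 30% | 14.6% | 18.0% | +3.4 |
| 4 mo | 20% | 50% | 0% | 38.2% | 43.4% | +5.2 |
| 4 mo | 20% | 50% | 30% | 38.2% | 41.7% | +3.5 |
| 4 mo | 20% | 100% | 0% | 38.2% | 43.5% | +5.3 |
| 4 mo | 30% | 50% | 0% | 38.2% | 46.1% | +7.9 |
| 6 mo | 30% | 50% | 0% | 52.7% | 59.6% | +6.9 |

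Over 10 to 40% discordance and medians of 2 to 6 months, Model B's shift ran from +1.5 to +11.9 points at 6 months and +0.6 to +14 at 12 months. Treating 30% beyond progression cuts it by about a third (3.5/5.2 = 0.67). In the 4-month, 20%, 50%, 0% row the median moved from 4.1 to 5.5 months, one step on the scan grid (week 18 to week 24).

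**Step 4: the case where it vanishes.** When discordant calls were made unrelated to later BICR PD, the 6-month shift was 0 if all started new therapy. With half starting, dating the rest at death still added about 0.7 to 4 points. No scenario went downward.

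**Step 5: scale.** Taking SE = sqrt(p(1 - p)/n) with n = 100 (the combination arm) and no censoring before 6 months:
- p = 0.146: sqrt(0.146 × 0.854/100) = 3.5 points
- p = 0.382: sqrt(0.382 × 0.618/100) = 4.9 points

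A shift of 5 points is about one SE or somewhat more, and the reported CI would not show it.

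**Step 6: the primary comparison.** With 150 and 100 subjects, ORR 10% and 23%, and pooled rate (15 + 23)/250 = 0.152:
- SE under the null = sqrt(0.152 × 0.848 × (1/150 + 1/100)) = 0.0463
- SE under the alternative = sqrt(0.09/150 + 0.1771/100) = 0.0487
- z = (0.13 - 1.96 × 0.0463)/0.0487 = 0.80, power 0.79 (Fisher exact 0.77)

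The stated 78% reproduces. PFS and DOR censoring does not enter it.

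**The case against.** **New therapy, not the scan rule, does much of the censoring.** This stands in part. Where all discordant subjects start new therapy, the whole shift passes through the subsequent-therapy rule. It also means that scanning on until BICR PD is not the remedy a reader might infer. With 25% discordance it removes nothing if all start new therapy before the next scan. If half do, it removes only about half (7.4 to 3.1 points at median 8 weeks; 7.3 to 3.8 at 13 weeks). Nor could a site follow such a rule while central reads are withheld.

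**The protocol has mitigations.** This stands as a limit on size. Treated-beyond-progression subjects keep being scanned, and Appendix 3, Section 4.1.2 asks for verification of equivocal progression, where readers are most likely to differ. But treatment beyond progression requires judged clinical benefit (4.5.7), so those who stop are the less well, and the verification is the investigator's own.

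**A sensitivity analysis belongs in the SAP.** An absent sensitivity table alone would not be a finding. Here the Protocol itself fixes the scan-stop and censoring rules, and their combination is the point. Withholding BICR reads from sites is not itself an error.

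**The stakes are low.** Largely right: PFS is secondary and descriptive, and only ORR is formally compared between the SCLC expansion arms.

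**Conclusion.** The mechanism follows from the Protocol's own rules for subjects who stop at an investigator PD the BICR does not share and who are not treated beyond progression. The upward direction is an expectation, conditional on such calls tending to precede BICR PD. The size, about 3 to 13 points in 6-month PFS at 15 to 35% discordance, rests wholly on assumed inputs. Treatment beyond progression lowers it by about a third at 30% uptake, and verification of equivocal PD would lower it further. DOR shares the censoring rule but was not simulated.

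A reader might infer that BICR PFS is shown to be biased by a known amount; the documents give no discordance rate to support that. A reader might also infer that the primary ORR is compromised because a response first seen at the stopping scan can never be confirmed. That is too strong: subjects treated beyond progression, or rescanned for equivocal PD, can still get the confirming scan. Any loss would be small and would lower ORR.

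This is a modest improvement to secondary estimates, worth making because it is cheap.

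**What to change.** In Sections 8.3.2 and 8.4.2.2, for each cohort with BICR endpoints, add a PFS and a DOR analysis in which investigator PD with no later BICR-evaluable scan usable for the endpoint (that is, before any new therapy) counts as an event on the date of that PD. Report it beside the BICR analysis, with investigator-BICR discordance by arm. In simulation it fell about 2 to 5 points below the full-follow-up 6-month PFS, so under these assumptions the two results bracket the truth.

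Separately, reconcile the scan-stop wording. Section 3.1.12 stops at investigator PD or discontinuation, with exceptions. Sections 5.3.1 and 5.4 use the later of the two and waive scans after new therapy. Table 5.1-7 of Revised Protocol 07d keeps scanning subjects without progression on study therapy after subsequent treatment.

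The cost is one more Kaplan-Meier table per cohort for each endpoint, a discordance count, and a companion estimate that is slightly pessimistic by construction. No new scans are needed.
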